Diarrhea \geq grade 3 or associated with dehydration (presumed secondary to drug – must rule out infectious causes)	Hold (interrupt dose) for remainder of cycle and hydrate. If diarrhea resolves to \leq grade 1, drug may be resumed with next cycle but at a one dose level reduction. If > grade 3 diarrhea recurs , repeat above and reduce by one dose level again. If again >grade 3 diarrhea recurs , patient will be removed from study .

Dyspepsia \leq grade 2	Initiate proton pump inhibitor or H2 blocker but proceed with current study drug dose. No dose reductions are required as long as symptoms resolve to \leq grade 1. If dyspepsia \leq grade 2 persists, decrease drug by one dose level. Continue with dose reductions if dyspepsia \leq grade 2 persists. When symptoms resolve to \leq grade 1, drug may be continued at the current dose level reduction.
Dyspepsia \geq grade 3	Hold (interrupt dose) until symptoms are controlled. Add proton pump inhibitor or H2 blocker. When symptoms resolve to \leq grade 1, drug may be resumed at a one dose level reduction.
Mucositis \leq grade 2	Initiate bicarbonate mouthwashes and mycostatin mouthwash. If mucositis \leq grade 2 persists, decrease drug by one dose level. Continue with dose reductions if mucositis \leq grade 2 persists. When symptoms resolve to \leq grade 1, drug may be continued at the current dose level reduction.
Mucositis \geq grade 3	Hold (interrupt dose) until symptoms are controlled. Initiate bicarbonate mouthwashes and mycostatin mouthwash. When symptoms resolve to \leq grade 1, drug may be resumed at a one dose level reduction.
Rash \leq grade 2	Hold (interrupt dose) until rash has resolved to \leq grade 1, then resume previous dose. If \leq grade 2 rash recurs, hold (interrupt dose) until rash has resolved to \leq grade 1, then resume dose at a one dose level reduction.
Rash grade 3	Hold (interrupt dose) for remainder of cycle. If rash has resolved to \leq grade 1, drug may be resumed at one dose level reduction. If grade 3 or higher rash recurs, patient will be removed from study.
Rash grade 4	Discontinue drug and patient will be removed from study.
Other non-hematologic toxicity assessed as study drug-related \geq Grade 3	Hold dose and follow at least weekly. When toxicity resolves to \leq grade 2 , restart at next lower dose level.

Progressive Multifocal Leukoencephalopathy (PML)

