5.7.1 Stopping Safety Criteria

5.7.1.1 Liver Chemistry Stopping Criteria

Liver chemistry threshold stopping criteria have been designed to assure subject safety and to evaluate liver event etiology during administration of investigational product and the follow-up period. The sponsor-investigator is to review all events which meet liver chemistry stopping criteria to determine if the event was due to;

- tumor lysis, disease related liver involvement
- concomitant chemotherapy
- other identified cause and to exclude drug induced liver injury (DILI) due to Ofatumumab

The criteria are relevant for all Ofatumumab studies because transient elevations in LFTs may be due to tumor lysis which is of clinical benefit, disease related liver involvement or due to other chemotherapy rather than drug induced liver injury from Ofatumumab. If the event is determined to be due to causes other than Ofatumumab DILI and improvement is observed after withdrawal of

Ofatumumab, rechallenge may be attempted if deemed appropriate by the sponsor-investigator and in addition to consent of the subject.

Investigational product will be stopped if any of the following liver chemistry stopping criteria is met:

1. ALT $\geq 8 \times \text{ULN}$
2. ALT $\geq 5 \times \text{ULN}$ for more than 2 weeks
3. ALT $\geq 3 \times \text{ULN}$ and bilirubin $\geq 2 \times \text{ULN}$ (>35% direct bilirubin, bilirubin fractionation required[‡])

[‡] **NOTE:** *If serum bilirubin fractionation not immediately available, study drug should be discontinued if ALT > 3xULN and bilirubin > 2xULN. Serum bilirubin fractionation should be performed if testing is available. If testing unavailable, record presence of detectable urinary bilirubin on dipstick, indicating direct bilirubin elevations and suggesting liver injury.*

When any of the liver chemistry stopping criteria is met, do the following:

- Immediately stop study treatment
- Hold Ofatumumab for two weeks, repeat liver chemistry testing at least twice weekly, and report to sponsor-investigator to discuss the possibility of re-challenging with Ofatumumab. *Note: The 2 week time point for stopping medication was chosen because it will distinguish from LFT elevations due to tumor lysis which should have resolved within this time period. Medication is interrupted and it is a clinical and patient decision if Ofatumumab may be re-started. The risk: benefit ratio is different in an oncology setting and an efficacious therapy may be life-saving.*

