- Report SAE to GSK within 24 hours
 - All events of ALT > 3xULN **and** bilirubin > 2xULN (>35% direct bilirubin) (or ALT > 3xULN and INR > 1.5, if INR measured; INR measurement is not required and the threshold value stated will not apply to subjects receiving anticoagulants), termed 'Hy's Law', **must be reported as an SAE (excluding studies of hepatic impairment or cirrhosis).**
 - NOTE: if serum bilirubin fractionation is not immediately available, study treatment should be discontinued if ALT > 3xULN **and** bilirubin > 2xULN. Serum bilirubin

fractionation should be performed if testing is available. If testing is unavailable, **record presence of detectable urinary bilirubin on dipstick**, indicating direct bilirubin elevations and suggesting liver injury.

Liver chemistry follow-up assessments are to be followed until liver chemistries resolve, stabilize or return to baseline values.

Liver Chemistry Follow-up Assessments; (these chemistry tests/ assessments below are to be performed at the time of the event and then continued and/or discontinued at the discretion/judgment of the sponsor-investigator; please refer to stopping criteria within this document below)

Viral hepatitis serology including:

- *Hepatitis A IgM antibody;*
- *Hepatitis B surface antigen and Hepatitis B Core Antibody (IgM);*
- *Hepatitis C RNA;*
- *Cytomegalovirus IgM antibody;*
- *Epstein-Barr viral capsid antigen IgM antibody (or if unavailable, obtain heterophile antibody or monospot testing);*
- *Hepatitis E IgM antibody*
- Serum creatine phosphokinase (CPK) and lactate dehydrogenase (LDH)
- Fractionate bilirubin, if total bilirubin >2xULN
- Obtain complete blood count with differential to assess eosinophilia
- Record the appearance or worsening clinical symptoms of hepatitis, or hypersensitivity, fatigue, decreased appetite, nausea, vomiting, abdominal pain, jaundice, fever, or rash
- Record use of concomitant medications, acetaminophen, herbal remedies, other over the counter medications, or putative hepatotoxins
- Increased alcohol use

The following assessments are required for subjects with ALT >3xULN and bilirubin >2xULN (.35% direct) but are optional for other abnormal liver chemistries:

- Anti-nuclear antibody, anti-smooth muscle antibody, and Type 1 anti-liver kidney microsomal antibodies
- Liver imaging (ultrasound, magnetic resonance, or computerized tomography) to evaluate liver disease.

Stopping Criteria:

- For subject meeting liver stopping criteria 1:

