 - A repeat of liver chemistries within 24 hours, liver event follow-up assessments and close monitoring
 - A specialist or hepatology consultation is recommended
 - Monitor subjects twice weekly until liver chemistries (ALT, AST, alkaline phosphatase, bilirubin) resolve, stabilize or return to within baseline values.
- For subjects meeting criteria 2 or 3:
 - A repeat of liver chemistries within 24 to 72 hours for repeat liver chemistries and liver event follow-up assessments
 - Monitor subjects weekly until liver chemistries (ALT, AST, alkaline phosphatase, bilirubin) resolve, stabilize or return to within baseline values
- After holding Ofatumumab for two weeks:
 - If the treatment is exhibiting efficacy **and** the subject wants to continue therapy after being informed of the results of liver chemistry testing, then the Ofatumumab may be re-started.
 - Liver chemistries and follow-up assessments should be monitored at a minimum of every 2 weeks until resolution, stabilization, or a return to baseline values, at which point monitoring should be continued per protocol
- Subjects with ALT >3xULN **but** <5xULN **and** bilirubin <2xULN without hepatitis symptoms or rash, and who may be monitored weekly for at least 4 weeks, then the following actions should be taken:
 - Subjects can continue Ofatumumab

- Weekly repeat of liver chemistries until they resolve, stabilize, or return to baseline values, then monitor liver chemistries as per protocol assessment schedule

If at any time the subject meets any of the liver chemistry stopping criteria, then proceed as described above

If after 4 weeks of monitoring, ALT<3xULN and bilirubin<2xULN monitor twice monthly until liver chemistries normalize or return to within baseline values

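### Section 5.7.1.1 calls ALT >3xULN with INR >1.5 Hy's Law, but no liver stopping criterion uses INR, and ofatumumab may expressly continue at ALT >3x to <5xULN

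*Combined protocol and SAP*

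**What the plan says.** All of the liver rules are in Section 5.7.1.1.

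- **Stopping criteria.** "Investigational product will be stopped if any of the following liver chemistry stopping criteria is met". Three follow: (1) ALT ≥8xULN; (2) ALT ≥5xULN for longer than 2 weeks; (3) ALT ≥3xULN with bilirubin ≥2xULN, more than 35% of it direct. INR is in none of them.
- **Actions once a criterion is met.** The first is "Immediately stop study treatment". Next come a two-week ofatumumab hold and an SAE report to the drug supplier within 24 hours.
- **Hy's Law.** The SAE item defines it in two forms: ALT >3xULN with bilirubin >2xULN (mostly indirect rises excluded by the 35% rule), or "ALT > 3xULN and INR > 1.5, if INR measured". The second form is limited: "INR measurement is not required and the threshold value stated will not apply to subjects receiving anticoagulants".
- **Continuation bullet.** For ALT above 3x but below 5xULN with bilirubin below 2xULN, in patients "without hepatitis symptoms or rash, and who may be monitored weekly for at least 4 weeks", the instruction is "Subjects can continue Ofatumumab". It ends with an override: "If at any time the subject meets any of the liver chemistry stopping criteria, then proceed as described above".

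Rules elsewhere also bear on the case. Section 5.5.4, Table 3 holds GSK2110183 for "Other non-hematologic toxicity assessed as study drug-related" of Grade 3 or higher. Section 5.5.2 delays a new cycle until drug-related toxicity is Grade 2 or lower. Section 5.5.3.1 then holds ofatumumab too; in mid-cycle it may go on if the investigator judges that it is not contributing. Section 5.7 lets the investigator stop for a harmful adverse event.

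**The concern.** The plan gives one name to two laboratory pictures and treats them differently. With raised bilirubin, Hy's Law ends dosing immediately. With raised INR at the same ALT, the only mandatory consequence in the liver section is a report, and the continuation bullet tells the site that ofatumumab may go on. A clinician who consults the section with a raised INR in hand is therefore given permission to continue.

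This concerns patient safety, not inference. Section 5.1.2 reports that AST and ALT abnormalities were the most frequent Grade 3 events with GSK2110183, so liver enzyme rises should be expected in this combination. The liver section says that tumor lysis can raise liver tests temporarily, which explains some tolerance. It gives no reason to treat the INR form more leniently than the bilirubin form.

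**Working it through.** There is no stated figure to reproduce, so the check applies the rules to test cases.

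**Inputs.** The three criteria, the Hy's Law definition and the continuation bullet (Section 5.7.1.1), and the general holds (Sections 5.5.2, 5.5.3.1 and 5.5.4).

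**Assumptions.** The CTCAE table is not reproduced in the protocol. I assume that Grade 3 ALT begins above 5xULN and that the INR rise is itself below Grade 3. Both are varied below.

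**INR form.** INR 1.8, no anticoagulant, bilirubin 1.5xULN, no symptoms, weekly monitoring possible, judged drug-related.

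| ALT | Criterion 1 (≥8x) | Criterion 2 (≥5x, >2 weeks) | Criterion 3 (bilirubin ≥2x) | Result as written |
|---|---|---|---|---|
| 4x | 4 < 8, no | 4 < 5, no | 1.5 < 2, no | Hy's Law SAE (4 > 3, 1.8 > 1.5); ofatumumab may continue (3 < 4 < 5) |
| 6x, ≤2 weeks | no | duration not met | no | Hy's Law SAE; no liver stop; general holds apply |
| 6x, >2 weeks | no | yes | no | Stop |
| 9x | yes | – | no | Stop |

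The override does not change the 4x row, because it refers only to the three criteria.

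**Bilirubin form.** With bilirubin 2.5xULN, 50% direct, and INR 1.0, criterion 3 is met in all four rows, so all four stop. The two forms differ only at 4x and at 6x for 2 weeks or less.

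**Varying the grading, for a drug-related event.**

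- *Grade 3 ALT begins above 3x, or the INR rise is Grade 3 or higher.* GSK2110183 is held. Ofatumumab is held at the start of a cycle, and in mid-cycle it depends on the investigator's view. The 3x to <5x gap is then only conditional.
- *Grade 3 ALT begins above 5x, INR below Grade 3 (base case).* No general hold applies at 4x, so the gap is clear. At 6x for 2 weeks or less the same general holds apply, so that band is a conditional gap.
- *Grade 3 ALT begins above 8x, INR below Grade 3.* No general hold applies at 4x or 6x. Only the 3x to <5x band carries an express permission to continue.

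**With the fix.** The INR form stops in all four rows. A patient on anticoagulants, or one whose INR is not measured, is managed as now.

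**The case against.** The strongest reply is about placement. The Hy's Law item stands in the list of actions to take once a stopping criterion has been met, and the first action in that list is to stop. Read that way, a Hy's Law event is one already stopped, and the drafters may have meant this. But placement adds INR to no criterion. The discontinuation note just after the INR clause names only ALT with bilirubin. Section 6.3.1 makes every stopping event an SAE, not the reverse. On either reading the continuation bullet has no INR condition.

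A second reply is that reporting more widely than one stops is a legitimate choice, and the section notes that risk and benefit weigh differently in oncology. That is fair as a general matter. It does not explain why one form of Hy's Law stops treatment and the other does not.

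A third reply is that the practical reach is small, and this stands. INR/PT is scheduled once, at screening (Section 2), and is optional in a liver event. The patient must also be off anticoagulants and free of rash and hepatitis symptoms. The clinician who ordered the INR may stop under Section 5.7, and the SAE report is still due within 24 hours.

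A reader might also infer that the gap exists however the event is graded. The documents do not support that: nothing says that the continuation bullet overrides Sections 5.5.2 and 5.5.3.1, so a drug-related Grade 3 event in this band would meet those holds.

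**Conclusion.** The inconsistency is real and narrow. In the band ALT >3x to <5xULN, with bilirubin <2xULN and INR >1.5 off anticoagulants, the liver section permits continued ofatumumab through an event that it calls Hy's Law. This rests on neither the ALT nor the INR rise being graded as drug-related Grade 3 or higher. If either is, the gap is conditional, as it is for ALT 5x to <8xULN lasting 2 weeks or less.

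Two stronger inferences should be avoided. The plan does not require dosing to go on: the bullet is permissive, and investigator judgment remains available in every band. Nor does the bullet authorize continued GSK2110183; it names only ofatumumab, although GSK2110183 is the drug with the liver signal cited in Section 5.1.2.

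The documents give no event rate and none is assumed; cases should be few. The change is worth making as a low-frequency safety correction. Sample size, endpoint and primary analysis are untouched.

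**What to change.** Make two wording changes in Section 5.7.1.1:

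1. Criterion 3, add: *or ALT ≥3xULN and INR >1.5, if INR measured and subject not receiving anticoagulants*.
2. Continuation bullet, after the bilirubin condition, add: *and INR ≤1.5 if measured (not applied to subjects receiving anticoagulants)*.

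The SAE item can stay as it is. At ALT exactly 3xULN the new criterion would stop treatment although the Hy's Law definition needs more than 3x; the bilirubin form already has this mismatch, and Section 6.3.1 makes any stopping event an SAE.

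No new test is needed. The cost is an occasional stop of both drugs, taking study treatment to mean both.

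- **Ofatumumab.** A two-week hold in the weekly phase loses up to 2 of 12 infusions (2/12 = 16.7%), since missed doses are not made up (Section 5.5.3.1). Rechallenge is already allowed.
- **GSK2110183.** Section 5.7.1.1 gives no restart time, and one should be stated. Planned dosing days are 10 + 18 × 28 = 514. A 14-day hold loses 14/514 = 2.7%, and a 28-day hold 28/514 = 5.4%. If the hold lasts to the end of a cycle or delays the next, Section 5.5.2 can also bring a one-level reduction, from 125 to 100 mg (25/125 = 20%).

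### Section 5.7.1.1 requires liver tests at least twice weekly during the two-week hold for every stopping criterion, then sets weekly testing for criteria 2 and 3

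*Combined protocol and SAP*

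**What the plan says.** All the relevant text is in Section 5.7.1.1 of the protocol, which defines three stopping criteria: (1) ALT at least 8×ULN; (2) ALT at least 5×ULN for more than 2 weeks; (3) ALT at least 3×ULN with bilirubin at least 2×ULN, more than 35% of it direct.

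- **General instruction.** It opens with "When any of the liver chemistry stopping criteria is met, do the following" and includes "Hold Ofatumumab for two weeks, repeat liver chemistry testing at least twice weekly". It makes no distinction between the criteria.
- **Criterion 1.** In the later list under the Stopping Criteria label: a repeat within 24 hours, then "Monitor subjects twice weekly until liver chemistries" settle.
- **Criteria 2 and 3.** In the same list, "For subjects meeting criteria 2 or 3" introduces "A repeat of liver chemistries within 24 to 72 hours" and then "Monitor subjects weekly until liver chemistries" settle.
- **After the two-week hold.** A separate bullet allows a restart under conditions and adds: "Liver chemistries and follow-up assessments should be monitored at a minimum of every 2 weeks".

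**The concern.** For criterion 1 the general and specific instructions agree. For criteria 2 and 3 they do not: a patient tested weekly is not being tested at least twice weekly. The criterion-specific line is the more detailed one, so staff could reasonably take it as the operative rule, and in doing so they would depart from the general one.

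The fortnight matters because restarting ofatumumab is decided at the end of it. The section explains that two weeks was chosen because elevations caused by tumor lysis should have cleared by then, so the results in that window inform the decision. Criterion 3 largely coincides with the combined event the section terms Hy's Law, for which it requires extra work-up, namely autoantibodies and liver imaging ("The following assessments are required for subjects with ALT >3xULN and bilirubin >2xULN"). That event is given the lighter schedule.

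Liver toxicity is also foreseeable here. Section 3.1 reports that the dose-limiting toxicities of GSK2110183 were reversible liver enzyme abnormalities, and Section 5.1.2 lists AST and ALT abnormalities as its most frequent Grade 3 events.

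**Working it through.** The plan states no figure to reproduce. The check compares the texts and counts tests.

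**Step 1: do the two rules cover the same patients?** The general instruction applies when any criterion is met, so it includes criteria 2 and 3. The weekly line names criteria 2 and 3. They overlap fully for those patients.

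**Step 2: do they cover the same period?** The general frequency is tied to the two-week hold. The weekly line follows directly on a repeat at 24 to 72 hours, so its block starts at the event and runs through the hold. The bullet on the period after the hold points the same way, because it gives that period its own minimum of every 2 weeks. It is weaker evidence, since weekly testing would also satisfy that minimum. No sentence delays the weekly rule to the end of the hold or sets an order of precedence.

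**Step 3: compare the frequencies.**

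| Criterion | General rule during hold | Criterion-specific rule | Consistent? |
|---|---|---|---|
| 1 | at least twice weekly | twice weekly | yes |
| 2 and 3 | at least twice weekly | weekly, after one early repeat | no |

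**Step 4: count panels over the 14-day hold for criteria 2 and 3.** The panel that triggers the hold is day 0 and is not counted.

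- General rule: at least 2 per week × 2 weeks = at least 4.
- Specific rule, weekly tests counted from the event: the repeat on day 1 to 3, then days 7 and 14, giving 1 + 2 = 3.
- Specific rule, weekly tests counted from the repeat: days 1 and 8 (next is day 15), or at the latest days 3 and 10 (next is day 17), giving 2. The third test falls after the hold either way.

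Shortfall against the floor: 4 − 3 = 1 to 4 − 2 = 2 panels per affected patient, at minimum.

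**Step 5: compare with patients who meet no stopping criterion.** The section also sets weekly testing for patients with ALT between 3 and 5×ULN and bilirubin below 2×ULN, without hepatitis symptoms or rash, who stay on ofatumumab. In Cycles 1 and 2, routine chemistry is already weekly (days 1, 8, 15 and 22 in the Section 2 schedule). Apart from the early repeat, the criteria 2 and 3 line therefore asks for no more than either of these.

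**The case against.** The strongest reply is that both rules can be obeyed at once. The general rule is a floor for the hold. The weekly line has no stated start and can outlast the hold, so testing twice weekly during the hold and weekly afterwards satisfies both. Graduated monitoring, with closer follow-up at ALT of at least 8×ULN, is a legitimate design, and the text does not forbid extra tests. That reading is sensible, and it is the one the fix adopts. But it is written nowhere, and following the criteria 2 and 3 line literally breaks the general rule.

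The second reply is that little turns on it, and much of this stands:

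- The gap is one or two panels, in a trial of 31 patients at one institution.
- Each liver event is reviewed by the sponsor-investigator, who also discusses any restart and can settle the frequency directly.
- The early repeat is required under the specific line, and unscheduled visits are allowed.
- Nothing in the documents shows that weekly testing plus the early repeat would leave the restart decision uninformed.
- The autoantibody and imaging requirements apply whichever frequency is used.
- The Hy's Law definition is not identical to criterion 3. It also admits ALT with a raised INR, and it uses strict inequalities where criterion 3 does not.

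These points limit the consequence. They do not remove the contradiction. Nor does the investigator's discretion in this section, which attaches to the listed follow-up assessments such as viral serology and CPK and does not relax the twice-weekly testing.

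**Conclusion.** The concern holds. For criteria 2 and 3, Section 5.7.1.1 contradicts itself on how often to test during the hold: at least 4 panels under the general rule against 2 or 3 under the criterion-specific line. The count assumes that the triggering panel is excluded, that the early repeat is included, and that weekly tests run either from the event or from that repeat. The finding that the weekly rule falls within the hold rests mainly on its position directly after the 24 to 72 hour repeat.

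This is an internal inconsistency in safety monitoring. Either way the drug is stopped, and the event is recorded as an SAE under Section 6.3.1. The documents do not say how many patients are expected to meet criterion 2 or 3, so the total number of missed tests cannot be estimated. The primary endpoint, sample size and error rates are untouched. It should be corrected because the conflict is plain, it includes the combined ALT and bilirubin event, and the correction is simple.

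**What to change.** In the criteria 2 and 3 entry of Section 5.7.1.1, keep the repeat at 24 to 72 hours and replace the weekly line with this rule: liver chemistries at least twice weekly during the two-week ofatumumab hold, then weekly until the existing end point for monitoring is reached. State that the early repeat may count as one of the first week's two tests. The hold then has at least 2 + 2 = 4 panels, which meets the general rule, and weekly testing afterwards is well within the every-2-weeks minimum for that period.

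The cost is one line of protocol text and one or two extra panels per affected patient compared with the criterion-specific line as it stands. Compared with the general rule there is no added burden, since it already requires those panels.

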- Positive serology for Hepatitis B (HB) defined as a positive test for HBsAg. In addition, if negative for HBsAg but HBcAb positive (regardless of HBsAb status), a HB DNA test will be performed and if positive the subject will be excluded. Consult with a physician experienced in the care and management of study patients with hepatitis B to manage and treat patients who are HBcAb positive. Initiate antiviral therapy, if required.
- Positive serology for hepatitis C (HC) defined as a positive test for HCAb, in which case reflexively perform a HC RIBA immunoblot assay on the same sample to confirm the result.
- Screening laboratory values:
 - platelets \leq 30 x 10⁹/L
 - neutrophils \leq 0.7 x 10⁹/L

estimated GFR <40mL/min as calculated by the Cockcroft Gault formula

total bilirubin ≥ 1.5 times upper normal limit (unless due to a known history of Gilbert's disease)

ALT ≥ 2.5 times upper normal limit

alkaline phosphatase ≥ 2.5 times upper normal limit

INR and PTT ≥ 1.5 times upper normal limit

- Pregnant or lactating women. Women of childbearing potential must have a negative pregnancy test at screening.
- Women of childbearing potential, including women whose last menstrual period was less than one year prior to screening, unable or unwilling to use adequate contraception from study start to one year after the last dose of protocol therapy.

Adequate methods of contraception include use of an intrauterine device with an additional barrier method (**diaphragm with spermicidal gel or condoms with spermicide**), double-barrier methods—(diaphragm with spermicidal gel **and** condoms **with spermicide**), partner vasectomy, and total abstinence. Oral or depot hormonal contraceptives are not reliable due to potential drug-drug interactions. (The same contraceptive guidelines apply for male patients with a partner who is a woman of childbearing potential)

- Male subjects unable or unwilling to use adequate contraception methods from study start to one year after the last dose of protocol therapy.

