In patients who develop HBV reactivation while receiving ofatumumab, immediately discontinue ofatumumab and start appropriate treatment for HBV, discontinue any concomitant chemotherapy the patient is receiving until the HBV infection is controlled or resolved. Due to insufficient data, no recommendations can be made regarding the resumption of ofatumumab after resolution of HBV in patients who develop HBV reactivation.

The risk of HBV infection and hepatitis can occur in patients who have not been previously exposed to HBV.

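### The liver rule in 5.7.1.1 lets ofatumumab continue, be rechallenged or restart without making hepatitis B status a condition, and its work-up does not name HBV DNA

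*Combined protocol and SAP*

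**What the plan says.** Three provisions in 5.7.1.1 allow further ofatumumab around a liver event.

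- **Rechallenge.** If the event has a cause other than ofatumumab liver injury and improves off the drug, "rechallenge may be attempted if deemed appropriate by the sponsor-investigator and in addition to consent of the subject".
- **Restart after the two-week hold.** If treatment is showing efficacy and "the subject wants to continue therapy after being informed of the results of liver chemistry testing, then the Ofatumumab may be re-started".
- **Continuation at ALT >3x to <5xULN.** For patients with bilirubin below 2xULN, "without hepatitis symptoms or rash, and who may be monitored weekly for at least 4 weeks, then the following actions should be taken". The two actions are "Subjects can continue Ofatumumab" and weekly repeat liver chemistries.

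The follow-up assessments in the same section list viral serology. For hepatitis B this is surface antigen and core IgM; for hepatitis C it is RNA. HBV DNA is not listed.

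The HBV reactivation text at the end of 5.5.4 orders ofatumumab stopped at once and treatment for HBV started. On resuming, it says that "no recommendations can be made regarding the resumption of ofatumumab after resolution of HBV in patients who develop HBV reactivation". It adds: "The risk of HBV infection and hepatitis can occur in patients who have not been previously exposed to HBV".

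HBV DNA is used elsewhere in the plan. At entry (5.2), "if negative for HBsAg but HBcAb positive (regardless of HBsAb status), a HB DNA test will be performed", and a positive result excludes the patient. Footnote 7 to the Schedule of Study Assessments then sets calendar HBV DNA tests for HBcAb-positive, DNA-negative patients.

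**The concern.** A rise in ALT is one way in which reactivation could first come to notice, and 5.7.1.1 is the section an investigator would open when it happens. That section decides the next ofatumumab dose on efficacy, the patient's wish, improvement off drug and liver chemistry. It does not ask for an HBV result or point to 5.5.4. The 5.5.4 rule, for its part, acts only once reactivation has been recognised.

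At stake is re-exposure, or continued dosing, in an HBcAb-positive patient before the test that the plan itself chose for that group has been repeated. Section 5.5.4 acknowledges that reactivation under this drug class can progress to liver failure and be fatal.

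**Working it through.** The plan states no figure on this point, so the check is a comparison of text followed by a comparison of intervals.

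**1. What each provision requires**

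| Provision | Conditions stated | HBV result required? | Refers to 5.5.4? |
|---|---|---|---|
| Rechallenge (5.7.1.1) | Non-ofatumumab cause, improvement, sponsor-investigator judgment, consent | No | No |
| Restart after hold (5.7.1.1) | Efficacy, patient's wish | No | No |
| Continue at ALT >3x to <5xULN (5.7.1.1) | Bilirubin <2xULN, no hepatitis symptoms or rash, weekly monitoring | No | No |
| HBV rule (5.5.4) | Reactivation has occurred | Not applicable | Does not mention 5.7.1.1 |

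On its wording, the rechallenge clause covers any improving cause other than ofatumumab liver injury, and that would include HBV. Section 5.5.4 does not close this gap, because declining to make a recommendation on resuming is not a prohibition.

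**2. Which HBV test is used where**

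| Setting | HBV DNA? |
|---|---|
| Entry, HBcAb-positive (5.2) | Yes |
| Calendar monitoring, HBcAb-positive and DNA-negative (footnote 7) | Yes |
| Liver event work-up (5.7.1.1) | Not named; HBsAg and core IgM only |
| Continue branch (5.7.1.1) | No viral test named in the branch |

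**3. Can a hold fall between calendar tests?**

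Inputs:
- Hold h = 14 days (5.7.1.1).
- Test spacing T from footnote 7: 14 days in month 1, 28 days in months 2 and 3, then 3 months, taken as 84 to 91 days.
- Assumptions: testing is counted from Cycle 1 Day 1, spacing is exact, and the hold is equally likely to start at any point between two tests.

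A hold can fall entirely between two tests when T > h. The chance that it contains no test is 1 − h/T.

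- Month 1: 1 − 14/14 = 0.
- Months 2 and 3: 1 − 14/28 = 50%.
- Later: 1 − 14/84 = 83% to 1 − 14/91 = 85%.

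These figures suit criteria 1 and 3. Criterion 2 needs ALT at or above 5xULN for more than 14 days before the hold, so more than 14 + 14 = 28 days pass before restart. The chance of no test over that span is then 0 through month 3. Later it is at most 1 − 28/84 = 67% to 1 − 28/91 = 69%.

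The +/- 4-day visit window can stretch a 14-day spacing to 14 + 4 + 4 = 22 days, so the zero for month 1 is nominal.

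These chances should not be averaged into one figure, because the documents do not say when liver events are likely to occur. A calendar test that does fall inside the hold still does not bind, because 5.7.1.1 does not make its result a condition.

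**The case against.** The case against is substantial, and much of it stands.

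- **Cause is reviewed.** The sponsor-investigator must review every stopping event for cause, and possible rechallenge must be discussed with that role.
- **HBV is tested.** HBsAg and core IgM are in the work-up, the list is worded as inclusive, and after the hold the follow-up assessments are monitored at least every 2 weeks until resolution. The sponsor-investigator may, however, discontinue individual assessments.
- **The group is narrow.** HBsAg-positive and HBV DNA-positive patients are excluded. HBcAb-positive patients have calendar DNA tests, and 5.2 calls for consultation with an experienced physician.
- **Other gates exist.** Section 5.5.2 requires drug-related infection and toxicity to settle before a new cycle. Section 5.5.3.1 lets ofatumumab continue during a mid-cycle GSK2110183 hold only if it is not thought to contribute to the toxicity.

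These safeguards make an oversight less likely. None of them prompts an HBV DNA test at the liver event or makes the next dose wait for its result.

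Four stronger readings are tempting but unsupported.

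- A reader might infer that the two sections give opposite orders. They do not: both stop ofatumumab once a stopping criterion is met, 5.5.4 is mandatory on reactivation, and restart is only permitted.
- A reader might infer that the listed serology would miss reactivation. The documents do not say so. They show only that the plan relies on DNA for HBcAb-positive patients, who are HBsAg-negative at entry.
- A reader might infer that a four-week run of weekly infusions could pass untested in an HBcAb-positive patient. On nominal spacing, a calendar test falls within any four weeks through month 3, although doses could precede it. After month 3, dosing is every 4 weeks.
- A reader might infer that ofatumumab must be held throughout the 3x to 5x band. The plan chose continuation with limits there, and overriding that is a debatable trade-off.

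**Conclusion.** The point holds as a missing link between two safety rules, together with an untriggered test. Followed as written, 5.7.1.1 can permit rechallenge, restart or continued dosing in an HBcAb-positive patient with no HBV DNA result since the liver event began. From month 2 a two-week hold can fall between scheduled tests. The period-specific chances in the working rest on exact spacing and random timing, and describe the calendar rather than patients.

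The documents give neither the HBcAb-positive fraction nor a reactivation rate, so the number of patients affected cannot be estimated. The point does not touch the primary analysis or the sample size. It merits consideration at the next amendment because the harm could be severe and the change is small.

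**What to change.** In 5.7.1.1:

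1. Add HBV DNA PCR to the follow-up assessments for HBcAb-positive patients who meet a stopping criterion. In HBcAb-positive patients with ALT >3x to <5xULN, draw it promptly without a mandatory hold, and stop ofatumumab if it is positive.
2. In the patients tested, allow rechallenge or restart only after a negative result.
3. State that if HBV reactivation is found, the rule in 5.5.4 takes precedence over the rechallenge, restart and continue provisions.

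The cost is a few lines of text, one blood test and possibly a short extra wait before restart in the patients tested. A wait that runs past a scheduled mid-cycle infusion and its visit window could cost that dose, since 5.5.3.1 does not allow missed ofatumumab doses to be made up.
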